## **8.3.11 COVID-19 infections**

COVID-19 infections occurring from the time of signature of the main study ICF until 30 days after discontinuation of study treatment should be reported as adverse events. Patients who test positive for COVID-19, but do not have any symptoms should be reported as 'asymptomatic COVID-19'. If COVID-19 is suspected but not confirmed by a diagnostic test, then 'suspected COVID-19' should be reported. The AE term for the 'suspected COVID-19' should be updated when the results of the diagnostic test are known to reflect the confirmed COVID-19 or alternative diagnosis (e.g. common cold, influenza etc).

### **8.3.12 Dysgeusia**

Loss of taste (dysgeusia) is an on-target adverse event known to occur with porcupine inhibition (Ng et al 2017, Janku et al 2015). According to CTCAEv5, there are only two grades of dysgeusia;

Grade 1 – Altered taste but no change in diet

Grade 2 – Altered taste with change in diet (e.g., oral supplements); noxious or unpleasant taste; loss of taste.

As dysgeusia is poorly characterized by CTCAE grade alone, site research personnel will complete a taste assessment (consisting of a specific set of questions and an oral examination) at screening for each patient enrolled, and for any patient who reports dysgeusia in response to the open question from the study site staff; 'Have you had any health problems since the previous visit/you were last asked?'. In such cases, the assessment will be performed at each visit until the adverse event has resolved. The information will be recorded and analysed as part of the overall safety objective of the study.

### **8.3.13 Adverse Events of Potential Interest (AEPI)**

As discussed in Section 2.3.1, Colitis events and Bone Toxicity events are classified as AEPIs for RXC004. This means that additional information will be captured on the case report forms for any CTCAE preferred terms that fall into these categories. These terms will be defined in the CRF Guidelines and reviewed at any update of the CTCAE definitions.

## **8.4 Overdose**

For this study, any dose of RXC004 greater than the daily assigned dose will be considered an overdose.

Investigators should be advised that any patient who receives an overdose should be monitored closely, managed with appropriate supportive care and followed up expectantly. There are no data regarding RXC004 overdose in humans. An overdose and AEs should be treated as per standard medical practice.

Dosing details should be captured in the eCRF. If the subject receives a dose of a study drug that exceeds protocol specifications and the subject is symptomatic, then the symptom(s) should be documented as AEs in the eCRF and, if serious, submitted to the Sponsor's designated safety contact on an SAE Report Form. Do not record the overdose as an AE if the subject is not symptomatic.

Please refer to the local label for management of nivolumab overdoses.

## 8.5 Human Biological Samples

Instructions for the collection and handling of biological samples will be provided in the study specific laboratory manual. Samples should be stored in a secure storage space with adequate measures to protect confidentiality. For further details on Handling of Human Biological Sample see Appendix C.

Samples will be stored for a maximum of 15 years from the date of the issue of the CSR in line with consent and local requirements, after which they will be destroyed/repatriated.

- Pharmacokinetic (PK) samples will be disposed of after the Bioanalytical Report finalization or six months after issuance of the draft Bioanalytical Report (whichever is earlier), unless consented for future analyses.
  - Pharmacokinetic samples may be disposed of or anonymised by pooling. Additional analyses may be conducted on the anonymised, pooled pharmacokinetic samples to further evaluate and validate the analytical method. Any results from such analyses may be reported separately from the Clinical Study Report (CSR).

### 8.5.1 Pharmacokinetics

RXC004 PK data will be summarised using descriptive statistics (N, mean, SD, median, min, max for all parameters, also geometric mean for  $C_{max}$  and AUC) to determine the pharmacokinetic behaviour of RXC004 on multiple dosing and to confirm relevant exposure to RXC004. This may also permit investigation of any significant metabolites. Venous blood samples (2 mL) for determination of concentrations of RXC004 in plasma will be taken at the times described in the schedule of assessments (Table 1 and Table 2). The date and time that the last dose of RXC004 was administered before the PK assessment day, the date and time of the dose of RXC004 administered on the PK assessment day and the date and time of collection of each sample will be recorded.

The date and time of collection of each sample will be recorded.

The timing of the PK samples may be adjusted during the study, dependent on emerging data, in order to ensure appropriate characterisation of the plasma concentration-time profiles. The total number of samples and the total volume of blood taken from each patient will not exceed that outlined in the Lab Manual.

If a patient misses any doses of RXC004 within 3 days of PK sampling, please contact the Sponsor representative as to any effect on the changes required on the timing of the PK assessments. All other assessments, including laboratory safety assessments, vital signs and RECIST should continue to be performed as per study plan, relative to baseline assessments.

Samples will be collected, labelled, stored and shipped as detailed in the Laboratory Manual.

### 8.5.1.1 Determination of Drug Concentration

Samples for determination of RXC004 concentrations in plasma will be analysed using an appropriate bioanalytical method. Full details of the analytical method used will be described in a separate bioanalytical report.

All samples still within the known stability of the analytes of interest at the time of receipt by the bioanalytical laboratory will be analysed.

In addition, the pharmacokinetic samples may be subjected to further analyses in order to investigate the presence and/or identity of drug metabolites. Any results from such analyses will be reported separately from the Clinical Study Report.

PK parameters will be estimated for each patient using WinNonlin® (Phoenix 64 V8 or higher) or suitable alternative. The following parameters will be derived, where appropriate, from the individual plasma concentration versus time profiles of RXC004.

**Table 17** **Definition of PK Parameters**

PARAMETER	DEFINITION
$C_{\max}$	The maximum observed concentration.
$t_{\max}$	The time at which $C_{\max}$ was apparent.
$AUC_{0-t}$	The area under the concentration versus time curve from time zero to the sampling time at the last quantifiable concentration ( $C_t$ ) at $t_{\text{last}}$ (the time of the last quantifiable concentration) calculated by the linear trapezoidal rule.
$\lambda_z$	The apparent terminal rate constant, estimated using the negative slope of the least square regression analysis of the log concentration versus time data for the terminal linear portion of the curve.
$t_{1/2}$	The apparent terminal half-life, calculated from $\log_e 2 / \lambda_z$ .
$AUC_{0-\infty}$	The area under the concentration-time curve estimated from time zero to infinity as the sum of the two areas: $AUC_{0-t}$ and $AUC_{\text{extrap}}$ , where $AUC_{\text{extrap}}$ is calculated as $C_t / \lambda_z$ .
CL	The systemic clearance calculated as: Dose/ $AUC_{0-\infty}$ .
$V_{ss}$	The apparent volume of distribution at steady state calculated as: Dose/ $AUC \times (AUMC / AUC_{0-\infty} - T/2)$ where T is the duration of intravenous injection.

Where appropriate the following RXC004 plasma pharmacokinetic parameters will be estimated. include

• $C_{\max}$	Maximum observed plasma concentration
• $t_{\max}$	Time to $C_{\max}$

• <math>C_{min}</math>	Minimum observed concentration across the dosing interval
• <math>\lambda z</math>	Terminal rate constant
• <math>t^{1/2}</math>	Terminal half-life
• AUC0-24 and from zero to infinity	Area under the plasma concentration-time curve from zero to 24 hours
• AUC0-t	Area under the plasma concentration-time curve from zero to the time of the last quantifiable concentration
• AUC0-∞	Area under the plasma concentration-time curve from zero to infinity
• AUCτ	Area under the plasma concentration-time curve across the dosing interval
• CL/F	Total plasma clearance after oral administration
• Vz/F	Apparent volume of distribution after oral administration
• Vss/F	The apparent volume of distribution at steady state
• MRT	Mean residence time
• Rac	Accumulation ratio based on AUC τ and C min after the first and the last dose
• Swing	(C max -C min )/C min

Dose proportionality of exposure parameters will be explored. In addition to dose normalisation of Cmax and AUC values.

Additional PK parameters may be calculated as appropriate.

Incurred sample reproducibility analysis, if any, will be performed alongside the bioanalysis of the test samples. The results from the evaluation, if performed, will be reported in a separate Bioanalytical Report.

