## 1.2 Schedule of Assessments

**Table 1** Arm A Schedule of Assessments

Treatment Phase	Table 1 – Arm A Schedule of assessments											
	Pre-treatment		RXC004 monotherapy			RXC004 + nivolumab combination j		Post-treatment				
	Pre-Screening	Screening	Cycle 0 (3-7 days)	Cycle 1 (28 day cycle)		Cycle 2 onwards (28 day cycles)	Pre-first Cycle	Cycle 1 onwards (28 day cycles)	IP Discontinuation	30 day Follow-up v	90 day Follow-up v	Survival follow-up
Window	n/a	-28 to -1	D1	D1	D15 +/- 1d	D1 +/- 3d		D1 +/- 3d	Within 7 days	+/- 3d	+/- 3d	q8w +/- 1wk
Pre-Screening informed consent	X											
CCI CCI CCI	X											
Genetic screening for RNF43/RSPO aberrations and MSI status t	X											
Main study informed consent		X										
Demography & baseline characteristics		X										
Smoking history		X										
Central MSI testing (if not completed in pre-screening)		X										

Table 1 – Arm A Schedule of assessments

Treatment Phase	RXC004 monotherapy											RXC004 + nivolumab combination j				Post-treatment			
	Pre-treatment		Cycle 0 (3-7 days)			Cycle 1 (28 day cycle)		Cycle 2 onwards (28 day cycles)		Pre-first Cycle	Cycle 1 onwards (28 day cycles)		IP Discontinuation	30 day Follow-up v	90 day Follow-up v	Survival follow-up			
Window	Pre-Screening	Screening	D1	D1	D15 +/- 1d	D1 +/- 3d		D1 +/- 3d	Within 7 days	+/- 3d	+/- 3d	q8w +/- 1wk							
CCI																			
CCI																			
CCI																			
CCI																			
CCI																			
CCI																			
CCI																			
CCI																			
Medical/ surgical history		X																	
Oral and dental assessment w		X	Oral assessment at each visit - only if patient reports dysgeusia																
Inclusion/ exclusion criteria		X						X k											
HepB, HepC and HIV testing		X																	

Table 1 – Arm A Schedule of assessments

Treatment Phase	Table 1 – Arm A Schedule of assessments											
	Pre-treatment		RXC004 monotherapy				RXC004 + nivolumab combination j		Post-treatment			
	Pre-Screening	Screening	Cycle 0 (3-7 days)	Cycle 1 (28 day cycle)		Cycle 2 onwards (28 day cycles)	Pre-first Cycle	Cycle 1 onwards (28 day cycles)	IP Discontinuation	30 day Follow-up v	90 day Follow-up v	Survival follow-up
Window	n/a	-28 to -1	D1	D1	D15 +/- 1d	D1 +/- 3d		D1 +/- 3d	Within 7 days	+/- 3d	+/- 3d	q8w +/- 1wk
CCI												
CCI												

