RECIST 1.1 assessments (by CT/MRI) n		X		On study tumour assessments should occur q8w +/- 1 week (relative to first dose of IP) for the first 56 weeks, followed by q12w +/- 1 week until RECIST1.1 radiological progression x				On study tumour assessments should continue q8w +/- 1 week (relative to first dose of IP) for the first 56 weeks, followed by q12w +/- 1 week until RECIST1.1 radiological progression q, x				If a patient discontinues for a reason other than progression then tumour assessments should continue q8w +/- 1 week (relative to first dose of IP) for the first 56 weeks, followed by q12w +/- 1 week until RECIST1.1 radiological progression					
CCI h (mandatory unless unavailable at site) i		X*		On study CCI h assessments should occur at week 8 and week 16 +/- 1 week relative to first dose of IP.			On study CCI h assessments should occur at week 8 and week 16 +/- 1 week relative to first dose of combination										
Vitamin D3 and Calcium supplements			Patients should commence 800 IU vitamin D3 (Cholecalciferol) daily and 1000-1500 mg calcium daily supplements from ICF signature until RXC004 discontinuation														
Denosumab dosing y			120 mg sc Denosumab once every month from C0D1 until RXC004 discontinuation														
RXC004 dosing m			X (2 mg single dose)	Continuous daily dosing (2 mg QD)			Continuous daily dosing (1.5 mg QD)										
RXC004 diary			X	Review at each visit													

Table 1 – Arm A Schedule of assessments

Treatment Phase	Pre-treatment		RXC004 monotherapy			RXC004 + nivolumab combination j		Post-treatment				
	Pre-Screening	Screening	Cycle 0 (3-7 days)	Cycle 1 (28 day cycle)		Cycle 2 onwards (28 day cycles)	Pre-first Cycle	Cycle 1 onwards (28 day cycles)	IP Discontinuation	30 day Follow-up v	90 day Follow-up v	Survival follow-up
Window	n/a	-28 to -1	D1	D1	D15 +/- 1d	D1 +/- 3d		D1 +/- 3d	Within 7 days	+/- 3d	+/- 3d	q8w +/- 1wk
Nivolumab dosing								480 mg q4w +/- 3 days o				
RXC004 PK f			X		X	X		X	X			
Concomitant medication		X	X	X	X	X	X	X	X	X	X	
Adverse events		X	X	X	X	X	X	X	X	X	X	
Taste assessment z		X	At each visit – only if patient reports dysgeusia									
Survival status and post-discontinuation anti-cancer therapy p										X	X	X

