### **4.4 Justification for Doses of RXC004 and Nivolumab**

Patients who enrol in Arm A RXC004 monotherapy will receive 2.0 mg RXC004 orally once a day in a fasted state. This dose was chosen using the predicted efficacious dose ranges from pre-clinical pharmacology models, preclinical and clinical target engagement assays, information from toxicology and toxicokinetic studies, and safety, efficacy and pharmacokinetics data from the Phase 1 study of RXC004 in patients with advanced solid tumours (NCT03447470).

Patients who receive combination therapy with RXC004 and nivolumab in Arm A or B will receive RXC004 1.5 mg orally once a day in combination with nivolumab 480 mg q4w. The RXC004 1.5 mg dose is supported by the available safety and PK data for this dose given in combination with nivolumab in the ongoing Phase 1 study RXC004/0001 (NCT03447470; see Sections 4.4.1.2 and 4.4.1.3). At a meeting held on 07 July 2022, the Phase 1 Safety Review Committee (SRC) determined that RXC004 1.5 mg in combination with nivolumab is a tolerated dose, based on safety and PK data (see Sections 4.4.1.2 and 4.4.1.3).

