### 6.2 Preparation/Handling/Storage/Accountability of Study Treatments

#### 6.2.1 RXC004

RXC004 will be supplied by Redx as 0.5 and 1.0 mg capsules. A complete description of the chemistry and formulation may be found in the Investigational Medicinal Product Dossier.

The Quality Control Standards and requirements for RXC004 study medication are described in separate release protocols/ Certificate of Analysis.

RXC004 is formulated as two dosage strengths capsules (0.5 mg and 1.0 mg), manufactured by Quay Pharma, [name]. The RXC004 capsules strengths are 0.5, 1.0 mg for oral administration. Stability testing of RXC004 is ongoing. Please refer to the current IMP label for the Expiry Date associated with the current shelf-life of the product.

Patients must fast (water to drink only) for at least 2 hours prior to taking a dose to at least 1-hour post-dose for all doses.

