2 STUDY OBJECTIVES

Objectives	Endpoints
Primary	
To assess the anti-tumour activity of RXC004 monotherapy and RXC004 + Nivolumab	Monotherapy: Disease control rate (DCR) using each patients Best Overall Response (BOR) according to RECIST 1.1 Combination: Objective response rate (ORR) using each patients BOR according to RECIST 1.1
Secondary	
To further assess the preliminary efficacy of RXC004 monotherapy and RXC004 + Nivolumab	% change in the sum of target lesions, duration of response (DoR), PFS, ORR (monotherapy) and DCR (combination) using investigator assessments according to RECIST 1.1 and OS
To assess the PK of RXC004 in monotherapy and in combination with Nivolumab	Maximum plasma concentration (Cmax) after Dose 1, Cmax at steady state, minimum observed plasma concentration (Cmin) at steady state as well as other relevant parameters (e.g. tmax, t ^{1/2} , λz, AUC _{0-∞} , CL/F, and Vz/F)
To assess the safety and tolerability profile of RXC004 monotherapy and RXC004 + Nivolumab combination	Incidence of AEs SAEs, dose reductions, interruptions and discontinuation and assessment of dysgeusia
Exploratory	
CCI CCI CCI CCI CCI	CCI CCI CCI CCI CCI CCI CCI CCI

CCI	CCI

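### Table 17 gives an intravenous Vss formula for an oral drug, and one clearance formula that would understate CL/F if used on the steady-state profile

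*Protocol*

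**What the plan says.** **Formulas.** Table 17 defines CL as "The systemic clearance calculated as: Dose" divided by AUC0-∞. It defines Vss as Dose/AUC multiplied by (AUMC/AUC0-∞ − T/2), "where T is the duration of intravenous injection". Neither row names a sampling occasion.

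**Second list.** Directly below, a further list names oral parameters without formulas: CL/F, Vz/F, Vss/F, AUCτ and MRT. It also names an accumulation ratio Rac, based on AUCτ and Cmin "after the first and the last dose". Both lists apply where appropriate.

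**Route.** Section 6.2.1 states: "The RXC004 capsules strengths are 0.5, 1.0 mg for oral administration". Section 4.4 says: "Patients who enrol in Arm A RXC004 monotherapy will receive 2.0 mg RXC004 orally once a day in a fasted state". Section 4.4 also has the combination dose taken orally.

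**Occasions.** The RXC004 PK row in both schedules (Section 1.2) marks C0D1, C1D15 and later visits. C0D1 is a single dose, followed by a Cycle 0 of 3 to 7 days before daily dosing starts. Section 4.4.1.3 treats C1D15 as steady state.

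**Endpoints.** The secondary PK endpoint (protocol Table 3, SAP Section 2) lists Cmax after Dose 1, then Cmax and Cmin "at steady state as well as other relevant parameters". Those other parameters include AUC0-∞, CL/F and Vz/F. Vss is not among them.

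**Redacted.** The half-life, the PK sampling times, and SAP Sections 3.2.2 and 4.11.4.

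**The concern.** The Vss row is the standard expression for an intravenous infusion, where T/2 removes the mean input time. For a capsule there is no infusion duration to enter. The mean input time is the mean absorption time, which plasma data after oral dosing alone do not identify. Neither Vss nor Vss/F can be validly derived from that row.

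The clearance row has two gaps. Without intravenous data, Dose/AUC estimates CL/F, not systemic clearance. And the row is a single-dose formula with no occasion attached. By C1D15 the patient has taken daily doses for two weeks, so an AUC extrapolated to infinity also contains drug left from those doses. The right divisor is then AUCτ, which the plan lists but does not connect to CL/F.

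CL/F and Vz/F are named secondary parameters in both arms, and neither has a printed formula of its own. An analyst looking for a clearance formula in the visible text finds only the single-dose one.

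**Working it through.** The documents give no CL/F or Vss value, so there is no planned figure to reproduce. The check asks what the printed formulas return on each occasion.

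**Inputs** (Table 12, steady-state geometric means):
- 2 mg alone: AUC0-24 931 h·ng/mL (n = 4), Cmin 26.8 ng/mL (n = 4).
- 1.5 mg with nivolumab: AUC0-24 706 h·ng/mL (n = 5), Cmin 13.6 ng/mL (n = 4).
- Half-life: redacted. Assumed 6 to 18 h.
- Absorption rate constant ka: not given. Assumed 0.5 to 2 per h, used only in the model checks.

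**Clearance, C0D1.** After a single oral dose with linear kinetics, AUC0-∞ = F·Dose/CL, so Dose/AUC0-∞ = CL/F exactly. Only the label is wrong there.

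**Clearance, C1D15.** At steady state AUCτ = F·Dose/CL, so CL/F = Dose/AUCτ:
- 2 mg: 2,000,000 ng / 931 = 2.15 L/h
- 1.5 mg with nivolumab: 1,500,000 ng / 706 = 2.12 L/h

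If the profile is extrapolated to infinity, AUC0-∞ = AUCτ + Cmin/λz, with λz = ln 2 / half-life. The share by which Dose/AUC0-∞ understates CL/F is (Cmin/λz) / (AUCτ + Cmin/λz).

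| Assumed half-life | 2 mg: Cmin/λz | Dose/AUC0-∞ (L/h) | Understated by | 1.5 mg + nivolumab: Cmin/λz | Dose/AUC0-∞ (L/h) | Understated by |
|---|---|---|---|---|---|---|
| 6 h | 232 | 1.72 | 232/1163 = 20% | 118 | 1.82 | 118/824 = 14% |
| 12 h | 464 | 1.43 | 464/1395 = 33% | 235 | 1.59 | 235/941 = 25% |
| 18 h | 696 | 1.23 | 696/1627 = 43% | 353 | 1.42 | 353/1059 = 33% |

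Because Vz/F = (CL/F)/λz, the same percentage carries over to Vz/F if that clearance is used.

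**Cross-check.** A one-compartment oral model dosed every 24 h gives an understatement of 7–8% at a 6 h half-life, 26–27% at 12 h and 40–42% at 18 h. The direction is the same and the upper end agrees. The lower end is softer, because the observed Cmin values are higher than a 6 h half-life would leave.

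**Vss with T = 0.** In the same model, AUMC/AUC after a single oral dose is 1/λz + 1/ka, so the result is the true volume times 1 + λz/ka. At 6 h and ka 0.5 this is 1 + 0.1155/0.5 = 1.23. At 18 h and ka 2 it is 1 + 0.0385/2 = 1.02. On the steady-state profile, with AUC0-∞ throughout, the ratio to the true value runs from 1.12 down to about 0.61. The error therefore changes sign with half-life and occasion.

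**The case against.** The strongest reply is that nothing tells the analyst to apply Dose/AUC0-∞ on C1D15. Table 17 defines CL, while CL/F, Vz/F and AUCτ sit in a separate oral list, and both lists carry the where-appropriate qualifier. The endpoint attaches steady state to Cmax and Cmin, not clearly to CL/F. The SAP's PK sections are redacted and may hold the correct definitions. This stands, and it makes the clearance error conditional. It does not supply the missing formula, and it does not rescue the Vss row, which fits no occasion in this study.

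Three stronger readings are tempting but unsupported:

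- **That planned CL/F is wrong in general.** It is not: the formula is right for the single C0D1 dose, and Cycle 0 separates that dose from daily dosing.
- **That the formula would create a false nivolumab effect.** A half-life taken from Cmax and Cmin in Table 12 gives λz = ln(68.5/26.8)/23 = 0.0408 per h (17 h) for 2 mg, and ln(76.4/13.6)/22.5 = 0.0767 per h (9 h) for 1.5 mg with nivolumab. The understatements are then 41% and 20%, which looks like a between-arm artefact. But two points on means of 4 to 5 patients are not a terminal slope, and the 2 mg Cmin has a CV of 134%. The same method gives 19% and 23% for 1 mg and 1.5 mg alone, and 15% for 1 mg with nivolumab. At matched doses, monotherapy and combination differ by only about 3 to 4 points. Table 12, which Section 4.4.1.3 cites for monotherapy and combination, reports Cmin, Tmax, Cmax and AUC0-24, which these formulas do not touch. No formal comparison of arms is planned.
- **That Rac cannot be derived.** The last dose can mean the last profiled dose. PK is also marked from Cycle 2 onwards, and the sampling times are redacted.

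**Conclusion.** The concern holds in a limited form. The Vss row is wrong as written for an oral drug, whatever the half-life. The clearance row is mislabelled and incomplete: correct on C0D1 as CL/F, but an understatement of roughly 14% to 43% if carried to C1D15.

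That range assumes half-lives of 6 to 18 h, linear kinetics, Cmin standing for the end-of-interval concentration, and Phase 1 geometric means from very small groups. It shows the order of size and does not predict this trial's results. Whether the error would occur in practice cannot be settled while the SAP's PK text is redacted.

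The reach is small. PK is a secondary objective summarised descriptively, Vss is not a named endpoint, and Cmax, Cmin, AUC0-24 and the efficacy endpoints do not depend on these rows.

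**What to change.** In Table 17:

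- Remove the intravenous Vss row, and do not derive Vss/F from it.
- Label clearance CL/F. Define it as Dose/AUC0-∞ on C0D1 and Dose/AUCτ on C1D15.
- Define Vz/F as the CL/F for that occasion divided by λz.
- Optionally, state Rac as C1D15 over C0D1.

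If the redacted SAP PK text already contains these definitions, align Table 17 with it. The cost is wording in the protocol and the PK specification. The same samples serve, and any parameter already calculated can be recomputed from the existing profiles.
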